3.0 Study Endpoints/Events/Outcomes

The primary endpoint is to conduct a clinical trial with 350 subjects (both non-smokers and smokers) to determine the effects of the watercress preparation on detoxification of environmental toxicants and carcinogens.

4.0 Study Intervention(s)/Investigational Agent(s)

We will freeze-dry approximately 2000 lbs of watercress to produce a powder (about 100 lbs, or 45.4 kg). Freeze-drying on the large scale required for this study will be performed by Van Drunen Farms. The resulting powder will contain the gluconasturtiin precursor to about 3 mg PEITC per gram (which will be released upon addition to H₂O.) Subjects will come to the clinic and receive a pre-filled sealed jar of

PROTOCOL TITLE: Watercress in Detoxification of Environmental Toxicants and Carcinogens

VERSION DATE: July 23, 2020

freeze-dried watercress powder and a pre-packaged flavoring product, which they will add to water and stir. Each jar of freeze-dried watercress (FDWC) will contain 125 g, two jars will be given to each participant for a total of 250 g. Dosing calculations will vary depending on the potency of PEITC for each batch of FDWC (a small sample will be taken from each batch and potency will be measured). An example calculation is as follows: a total of forty-two 4.4-gram portions will be taken over the 2-week period; each 4.4 gram portion will release about 13.2 mg of PEITC. The 2-week supply will provide for an extra 14 doses for a total of 56 doses ($4.4 \times 56 = 246$). For the placebo, we plan to use maltodextrin, which is a polysaccharide and does not contain glucosinolates, and the same flavoring product used to prepare the watercress drink. Subjects will prepare the placebo drink in the same way as the watercress drink. Each jar of maltodextrin will contain 250 g, one jar will be given to each participant. A total of forty-two 4.4-gram portions will be taken over the 2-week period and each container will hold an extra 14 doses for a total of 56 doses ($4.4 \times 56 = 246$).

Flavoring Product

We will use a commercially available flavoring product such as Crystal Light or SweetLeaf Water Drops™. Participants will mix a pre-determined amount of flavoring product with the FDWC or placebo.

[figure not shown]
Drink Preparation

Freeze-dried Watercress. Participants will be instructed to mix one scoop (73 mL) of FDWC with 16 oz of water and stir for 30 seconds, then let the mixture rest for 2 minutes. Next, they will add in the flavoring product and stir for 10 seconds. Participants will be asked to finish the drink within 10 minutes of mixing.

Maltodextrin. Participants will be instructed to mix one scoop (11 mL) of maltodextrin with 16 oz of water and stir for 30 seconds, then let the mixture rest for 2 minutes. Next, they will add in the flavoring product and stir for 10 seconds. Participants will be asked to finish the drink within 10 minutes of mixing.

5.0 Procedures Involved

The study will be a randomized, placebo-controlled, single-blind, phase II clinical trial with a crossover study design. Participants will be assigned to active or placebo study product for 14 days, then undergo a 4 week wash-out period, and will then be crossed over to the other product for another 14 days (see **Figure 2**). During the treatment phase, subjects will consume the watercress beverage or placebo, 3 times per day. The target dose will be 40 mg/day of PEITC, as in our previous study. Urine, oral swabs, saliva, and blood will be collected.

Screening Visit

This study will be conducted at two Minnesota sites: University of Minnesota Twin Cities and Hormel Institute, which is a part of the University of Minnesota. Subjects will first undergo a prescreening visit, which will be conducted via phone or online REDCap survey. Those who meet the eligibility criteria will be invited to complete a virtual screening visit (completed via secured video-conferencing link). In order to follow guidelines set forth by the Centers for Disease Control and the University of Minnesota, a significant portion of the study procedures will be completed remotely.

During the virtual screening visit, we will explain, that in the trial, subjects will be asked to use a drink prepared from watercress or an inert substance (placebo) that will be provided by us. The order in which they receive the watercress or placebo product will be randomized. Each product will be used for a period of 14 consecutive days with a 4-week interval separating the two periods. An electronic informed consent (e-consent) will then be obtained. Following consent, study participants will be asked to complete questionnaires to assess demographics, medical and medication history, psychiatric status and substance abuse history (see **Table 4**). Our Licensed Medical Professional, will review these health questionnaires for consistency and eligibility for the study. Tobacco users will be asked to complete a tobacco use history form that assesses amount and frequency of tobacco use. Eligible participants will then be scheduled for a clinic visit and asked to refrain from eating any cruciferous vegetables during the course of the study. (Cruciferous vegetables are the only other major source of isothiocyanates that could affect the study results.) A list and pictures of cruciferous vegetables will be provided to each participant. Participants will be provided a urine cup (via mail) and asked to collect their first morning urine on the day of their next clinic visit. A reminder call or text will be sent to the participant prior to this visit.

Experimental Period

PROTOCOL TITLE: Watercress in Detoxification of Environmental Toxicants and Carcinogens

VERSION DATE: July 23, 2020

Study design. Participants will be asked to attend clinic visits on days 0 (the day of product distribution), 4 (± 1 day), 7 (± 1 day) and 14 (± 1 day) for each of the periods they are receiving product and weekly during the 4 week washout between periods (see **Figure 2**). We use a 4-week washout period because the 1-week washout in our preliminary studies may not have been sufficient [11]. Each visit is composed of three parts and will be completed in a single day. Part 1: Prior to the clinic visit the participant will collect their first morning void urine. Part 2: In a virtual visit, participants will be asked to complete multiple online surveys (see **Table 4**). Part 3: Participants will drop off their first morning void urine (also used to test for pregnancy) at the research clinic (University of Minnesota – Tobacco Research Programs, [name]). Blood (once allowed), blood pressure, saliva, oral rinse, and buccal cells will be collected. After this collection, participants will be provided with either the watercress powder or the placebo and the flavoring product. Subjects will be given written instructions on how to add the watercress/placebo powder and flavor product to water and will also be provided a link to a video with instructions. They will be provided three different flavors from which they can sample. At the Day 4 visit, they will be asked to choose one of the flavors to be used during the rest of this phase. They will be asked to drink the formulation at breakfast, lunch and dinner. Participants will receive one jar of the FDWC on day 0 and the second jar on day 7. Participants will receive one jar of maltodextrin on day 0, which will last until the end of the study. A log will be kept of the products that are dispensed and any amounts unused. At the end of each two-week period (or end of study participation, whichever comes first), we will ask all participants to return any unused product. Compliance of use of the study products will be determined by the product accountability log and biochemical verification (e.g., urinary PEITC-NAC and total isothiocyanates). Participants will be provided standardized counseling about the importance of using the assigned products as directed and if procedural compliance is an issue, the research assistant will discuss the obstacles and develop a plan to overcome these obstacles. Participants will also be provided a urine collection cup, dietary intake log and dosing log at each visit.

Biospecimen collection. All collection containers will be labeled with study number, subject number, collection date and type of biological sample (urine, blood, saliva, buccal cells). At each clinic visit, first morning void urine samples will be collected and participants will be asked to submit saliva and oral cells. Participants will be asked to brush their teeth in the bathroom at the beginning of the visit by using a provided commercial individually packed pre-pasted toothbrush (ReadyBrushTM) and asked to not eat, drink, smoke or chew gum for 5 min prior to obtaining oral cells. Saliva samples will be collected by asking the participant to spit in a sterilized 10 ml tube. These samples will be frozen at -20 °C for possible future oral microbiome studies. Oral cells will be collected by first, doing an oral rinse. Participants will squirt 15 mL of saline solution into their mouths and swish for 45 seconds. The oral rinse sample will be expectorated back into a 50 mL tube. After completing the rinse, participants will scrape the oral mucosa inside the mouth with a cytobrush. Two cytobrushes will be used on each subject to collect two separate samples from the left and the right inner cheek. After scraping the mucosal surface, each cytobrush will be immediately placed into a separate pre-labeled sterile polypropylene tube containing 5 mL of saline, swirled for a

PROTOCOL TITLE: Watercress in Detoxification of Environmental Toxicants and Carcinogens

VERSION DATE: July 23, 2020

few seconds, and tapped against the walls of the tube to ensure the cells are transferred from the brush to the saline. Oral cells will be stored at -20°C for DNA isolation and research in future years of this study, which may include analysis for protein expression, including GSTP1. The use of oral cells for protein expression studies has been described [70].

Blood collection. Blood will not be collected until allowed per University policy. Once allowed by the University, blood collection will occur in two phases. Phase 1: One tube of blood will be collected (8 mL purple top). Depending on when blood collection is allowable, it will be collected on day 0 or if the participant has already completed the study, we will contact them again to have them come to the clinic for a one time blood draw. Phase 2: Blood will be collected on days 0, 7 and 14. Two tubes of blood (8 mL each, purple top) will be drawn by a trained technician. Blood samples will be used for DNA and protein isolation. The DNA will be used for genotyping (described under Specific Aim 3) and the protein reserved for possible future studies of expression of GSTP1 and other proteins. Protein will be isolated from peripheral blood mononuclear cells as described [69].

Sample preparation Blood collected into purple top tubes will be processed within 12 h of phlebotomy. Samples should remain on ice until processing. The tubes will be centrifuged at 2500 × g for 15 min in a refrigerated centrifuge to separate plasma, buffy coat, and red blood cells. The separated components will be transferred into cryogenic vials, labeled (with information described above) and stored in a -80 °C freezer. For genetic analysis, genomic DNA is purified from buffy coats using a PureGene Blood Kit (Gentra Systems, Minneapolis, MN) according to the instructions provided by the manufacturer. DNA samples are aliquoted into 96-well plates using robotic equipment to minimize human error. The extracted DNA samples will be used for the determination of *GST* genotypes. The urine samples will be aliquoted into cryotubes and frozen at -20 °C. Tubes with buccal cell samples will be centrifuged at 2500 × g for 15 min to pellet the cells and the supernatant will be discarded. The cell pellets will be washed by adding 1 mL of pH 7.4 buffer, swirling the tube gently, repeating the centrifugation, and discarding the buffer. The washed buccal cell pellet will be re-suspended in 100 µL cold buffer, transferred into a pre-labeled cryovial, and stored at -20 °C. Throughout the study, biological samples (blood, buccal cells, urine, saliva) will be collected, labeled and registered on our Biomarker Website. The Hormel Institute will send batches to the Masonic Cancer Center, University of Minnesota, to be stored in the Biorepository with de-identified information. The Hormel Institute and Masonic Cancer Center Biorepositories have established policies and procedures consistent with NCI guidelines. Samples will be stored until fully used, no longer usable, or destroyed upon subject request. A discussion of the storage, future use, and sharing of samples will be presented in the informed consent for this study. A Data and Biospecimen Sharing Plan is also provided below.

Other measures Health changes, medication use, and adverse events since the last visit will be determined, vital signs measured and ingestion of any cruciferous vegetables

PROTOCOL TITLE: Watercress in Detoxification of Environmental Toxicants and Carcinogens

VERSION DATE: July 23, 2020

assessed. Among tobacco users, specific type of tobacco product use and amounts of use will be determined using the timeline follow-back method.

Table 4. Procedures for each visit

	Pre-Screening	Screening	Clinic visits during the 14 days of study product use (days 0,4,7,14)	Clinic visits (weekly) during one-month wash-out period
Telephone screening (remote)	X			
Consent form (remote)		X		
Screening questionnaires (remote) ^{a,b}		X		
Body Mass Index (remote)		X		
First urine void			X	X
Urine Pregnancy Test (in-person clinic)		X		
Blood draw (in-person clinic) ^c			X	X
Oral cell collection (in-person clinic)			X	X
Saliva collection (in-person clinic)			X	X
Vital signs (in-person clinic)	X		X	X
Health changes (remote)			X	X
Adverse effects (remote)			X	X
Medications questionnaire (remote)			X	X
Affect liking scale (remote) ^d			X	
Dietary intake Log (remote)			X	X
Study product dose log (remote)			X	
Dispense study products (in-person clinic)			X	

a Demographics, Medical History; Medications Questionnaire, PRIME MD(b), Michigan Alcohol Screening Test(b), Drug Abuse Screening Test(b), and Tobacco Use History for those who are tobacco users.

b Questionnaires will only be administered if the participant responds 'yes' to related items in the Medical History Questionnaire

c Blood will be only be drawn once allowable by the University.

d Affect liking scale will be done on Day 14 for each study product use period

PROTOCOL TITLE: Watercress in Detoxification of Environmental Toxicants and Carcinogens

VERSION DATE: July 23, 2020

Description of Measurements at the Research Clinic

Screening measures. 1) *Demographics* such as age and gender, race, ethnicity, income, current occupation and usual occupation; 2) *Medical history and current health status* for current diagnoses, symptoms and past health problems; 3) *Medications Questionnaire* to rule out medications that affect the metabolism of targeted constituents; 4) *Prime MD* for depression and anxiety symptoms [71]; 5) *Michigan Alcohol Screening Test Short form (SMAST)* [73]; and 6) *Drug Abuse Screening Test (DAST)* [74]. For those who are tobacco users, we will administer a Tobacco Use History that assesses amount and frequency as well as duration of tobacco use [11]. The following measures comprise the *Biomarker modifier questionnaires* (measures of factors that may moderate biomarkers at each clinic visit): 1) *Dietary Intake* assesses consumption of cruciferous vegetables since the prior visit; 2) *Medications Questionnaire* to assess any changes in medications taken since last visit and to determine use of any drugs that may affect the Nrf2 pathway; 3); *Safety measures: Health Changes and Adverse Events Scale* to assess the nature, severity, duration, action taken, and outcome of any adverse events. *Vitals:* Blood pressure and heart rate will be measured.

Information about each subject will be entered into a database by the Study Coordinator. Each subject will be coded with a unique number, and only these coded ID's will be entered into the database. All raw data will be kept in locked file cabinets. Only the Project Manager, Study Coordinator and Principal Investigators will have access to individually identifiable private information about participants. Coded ID's will be used throughout the study by all the researchers involved. While all the samples and information will be collected specifically to achieve the goals of this proposal, de-identified individual subject data and back-up samples may be available to other researchers for research purposes after our study is complete. Permission will be obtained from participants to allow de-identified biosamples to be stored in a biorepository for future analyses of biomarkers or genotyping. Standard operating procedures will be developed, as in our previous studies. A tracking database will be developed to follow each participant from enrollment to study completion. A detailed study manual will be developed with step-by-step instructions for interviewers and phlebotomists. All staff will be trained in the procedures and visits will be made to the Hormel Institute site to monitor the case report books and ensure that the protocol is strictly followed.

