Any SAE occurring after the participant has signed the consent form and until the last encounter with the participant will be reported. All AEs will be summarized by presenting, for each treatment group, the number and percentage of participants who experienced any AE, the number reporting AEs in each body system and the number of AEs by type. Any other information collected (e.g., severity or relatedness to study product) will be listed as appropriate. A summary of clinically relevant toxic events, such as AEs leading to death or rated as SAEs, those with a suspected relationship to study product, or AEs requiring further medication or non-drug therapies will be provided. Reports will be reviewed regularly by the study investigators.

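### The trial is labelled single-blind without saying who is blinded, and the two products as described would not keep participants blind

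*Combined protocol and SAP*

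**What the plan says.** Section 5.0 gives the design: "The study will be a randomized, placebo-controlled, single-blind, phase II clinical trial with a crossover study design". After the washout, participants "will then be crossed over to the other product for another 14 days", so each person uses both products. Neither section 5.0 nor the statistical section (15.0) says which party is blinded.

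Section 4.0 describes the products. For watercress, "Participants will be instructed to mix one scoop (73 mL) of FDWC with 16 oz of water"; for placebo, "Participants will be instructed to mix one scoop (11 mL) of maltodextrin with 16 oz of water". Each watercress jar "will contain 125 g, two jars will be given to each participant for a total of 250 g", whereas "Each jar of maltodextrin will contain 250 g, one jar will be given to each participant". Section 5.0 adds, for watercress, "Participants will receive one jar of the FDWC on day 0 and the second jar on day 7"; the single placebo jar is handed out on day 0.

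At the screening visit (section 5.0) participants are told that one drink is made from watercress, that the other is inert, and that the order is randomized.

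The masking measures described are a common flavouring and common mixing steps (section 4.0) and an alphabetic treatment code held by the Project Manager (section 15.0). Matching of powder volume, packaging, colour, smell or taste is not described, and neither is any check of what participants believe they received.

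On safety, section 17.0 says: "All AEs will be summarized by presenting, for each treatment group, the number and percentage of participants who experienced any AE". Table 4 schedules a liking scale on day 14 of each product period.

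**The concern.** A single-blind, placebo-controlled label tells a reader that participants' expectations are held equal between the two periods. Here the person who is presumably blinded opens the jar, measures the powder and mixes the drink three times a day, and does so with both products. The differences are large enough to notice without any special effort.

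Urinary mercapturic acids reflect exposure as well as conjugation. Someone who knows the current product may smoke, eat or adhere differently in that period, and the change would then be read as detoxification. Section 15.0 relies on within-subject subtraction to remove subject-specific factors. That works for stable factors but not for behaviour that follows the product. The mixed model in section 15.0 includes baseline cigarettes per day, not cigarettes per day in each period. Self-reported adverse events (section 13.0 anticipates flatulence, bloating and nausea) and liking scores are open to expectation directly.

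The effects that section 15.0 uses to argue for good power came from a trial that section 2.0 (Preliminary Studies) describes as double-blind. The current label obscures the fact that this trial has less protection.

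**Working it through.** **Inputs.** Scoops of 73 mL and 11 mL, jars of 2 × 125 g and 1 × 250 g, and a 4.4 g portion (section 4.0; for watercress this is an example that varies with batch potency). Three drinks a day and the dispensing days (section 5.0). About 100 smokers among 400 enrolled (section 10.0), a fraction of 100/400 = 0.25, as in section 15.0.

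**Assumptions not in the documents.** Product knowledge shifts every smoker's exposure by 10% to 20% in the same direction, non-smokers do not shift, and mercapturic acids are proportional to cigarettes smoked. Neither the size nor the direction of such a shift is known.

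**1. The plan's own figure.** 4.4 g × 56 doses = 246.4 g, stated as 246. It reproduces.

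**2. How different the products are.**

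| | Watercress | Placebo | Arithmetic |
|---|---|---|---|
| Scoop | 73 mL | 11 mL | 73/11 = 6.6 |
| Powder per day | 219 mL | 33 mL | 3 × scoop |
| Bulk density | 0.060 g/mL | 0.40 g/mL | 4.4 g / scoop |
| Doses per jar | 28.4 | 56.8 | jar mass / 4.4 g |
| Powder volume per jar | about 2,070 mL | 625 mL | doses × scoop |
| Jars and days | two, days 0 and 7 | one, day 0 | as stated |

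The 6.6-fold ratio does not depend on the portion mass. The densities and jar volumes do.

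**3. What each period reveals.** In period 1 a participant sees one product only, so scoop and jar count have no comparator. The participant does know that one of the two products is watercress, and is handling either 73 mL of freeze-dried vegetable powder or 11 mL of maltodextrin per drink. A correct guess is plausible. In period 2 the same person can compare scoop, jar count and the presence or absence of a day-7 hand-out with the previous period, and a correct guess is very likely.

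**4. Size of a behavioural shift.** The outcomes are analysed on the log scale. If smokers shift by a factor 1 + s and non-smokers do not shift, the all-subject geometric-mean ratio is multiplied by (1 + s)^0.25.

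- s = 0.10: 1.10^0.25 = 1.024, or about 2.4%.
- s = 0.20: 1.20^0.25 = 1.047, or about 4.7%.

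Among smokers alone the watercress-placebo ratio moves by the full 10% to 20%.

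**5. The genotype comparison.** Let d be the true log-ratio in a genotype group and b the mean behavioural shift. If b is the same in both groups, (d_null + b) − (d_positive + b) = d_null − d_positive. The shift cancels in expectation.

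**The case against.** The case against rests on five arguments.

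- **Nobody says participants are the blinded party.** This is true, and the point is conditional on the usual meaning. If someone else was meant, the protocol still has to say so.
- **Blinding is not shown to fail.** A reader might infer that participants are certain to know their product from the first dose. The documents do not support that: period 1 has no comparator, and they describe neither colour nor taste. Identification is an inference, strong only by period 2.
- **The laboratory is already masked in practice.** A reader might infer that it is unblinded because no sentence says otherwise. That goes too far. Containers carry study number, subject number, date and sample type, not product (section 5.0, Biospecimen collection). Researchers use coded identifiers, samples sent for analysis are de-identified (section 6.0), and the Project Manager holds the code. One gap stands: urinary PEITC-NAC is measured to verify compliance (sections 5.0 and 11.0) and could reveal the product to anyone who sees it alongside the mercapturic acid results.
- **The bias is small.** It is tempting to set a 10% to 20% shift beside the 15.1% rise in 3-HPMA reported in section 2.0 and call them comparable. That rise was an average over a trial of smokers only. Here about a quarter are smokers, so the all-subject shift is 2.4% to 4.7%. The comparison is fair only within smokers. Tobacco use and cruciferous intake are also recorded during follow-up, so a shift could be detected, although the listed model does not adjust for smoking by period.
- **The emphasized analysis is the genotype comparison.** Section 15.0 concentrates on it, and step 5 shows that it is largely protected. This stands, provided behaviour is unrelated to genotype.

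Adverse events are already summarized as counts and percentages, so what is missing there is a label and not a different analysis.

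**Conclusion.** The concern holds in conditional form. On the usual meaning of single-blind, the trial states a property that its own product descriptions do not support, and on any other meaning the blinded party is missing from the text.

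The consequences fall on the overall watercress-placebo effect, the watercress-placebo ratio among smokers, and the adverse-event and liking comparisons. Under the assumed shift the size is about 2.4% to 4.7% over all subjects and 10% to 20% among smokers. These figures illustrate sensitivity and are not an estimate of bias.

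A reader might conclude that the trial's main inference is compromised. The documents do not support that: the main outcomes are laboratory measurements, randomization is unaffected, and a shift unrelated to genotype cancels in the genotype comparison. The matter should be corrected because the label would otherwise be carried into the report and overstate the protection against bias.

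**What to change.** 1. In section 5.0, replace single-blind with an accurate statement that participants are not effectively blinded. Claim laboratory masking only if mercapturic acid results are released on the existing coded samples before the PEITC-NAC results and the allocation code are linked to them.
2. Remove the avoidable cues by supplying placebo as two jars, on days 0 and 7, with the amount taken unchanged. Section 5.0 already schedules a day-7 visit in both periods, so no visit is added. Acknowledge that the powder-volume cue remains: at the example portion, 125 g of placebo occupies 125/0.40 = about 310 mL, against about 2,070 mL for 125 g of watercress.
3. State in section 17.0, and wherever the liking scale is reported, that comparisons between products are unblinded.

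The cost is protocol wording, an agreed order for releasing laboratory results, and one packaging change. The downside is a less favourable design label.
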